17. SAFETY OUTCOMES

All outputs for safety outcomes will be based on the Safety Analysis Set.

There will be no statistical comparisons between the treatment groups for safety data, unless otherwise specified within the relevant section.

17.1. Adverse Events

Adverse Events (AEs) will be coded using MedDRA central coding dictionary, Version 26 or higher.

Treatment emergent adverse events (TEAEs) are defined as AEs that started or worsened in severity on or after the first dose of study medication.

The number and percentage of participants with at least 1 solicited AE (local, systemic and any) during the 7-day solicited period will be tabulated by treatment group with exact 95% CI after each vaccination and overall.

The number and percentage of participants reporting individual solicited local and systemic AE during the 7-day solicited follow-up period will be tabulated by treatment group and severity grade with exact 95% CI as follows:

- Over the 3 doses, the percentage of subjects with the symptom and its exact 95% CI
- At each study dose (visit), the percentage of subjects with the symptom and its exact 95% CI

Counting rules for occurrences of solicited adverse events: When the occurrences of solicited adverse events are summarized, each event recorded as having occurred during a specific period will be counted as only one occurrence regardless of the number of days on which it occurred. For a given participant and the analysis of solicited symptoms within 7 days post-vaccination, missing or non-evaluable measurements will not be replaced. Therefore, the analysis of the solicited AEs includes only vaccinated subjects for doses with documented safety data (i.e., diary completed). More specifically the following rules will be used:

- Participants who documented the absence of a solicited symptom after one dose will be considered not having that symptom after that dose.
- Subjects who documented the presence of a solicited symptom and fully or partially recorded daily measurement over the solicited period will be included in the summaries at that dose and classified according to their maximum observed daily recording over the solicited period
- Subjects who documented the presence of a solicited symptom after one dose without having recorded any daily measurement will be assigned to the lowest intensity category at that dose (i.e. 38°C for fever or

Document: \\dccar2dnetvnasc01p-lan1.quintiles.net\cp_ops\BIOS\MinervaX\GBS-
NN_NN2\MVX0006\Biostatistics\Documentation\SAP

Author: [REDACTED] Version Number: 1.0

Version Date: 19APR2024

Template No.: CS_TP_BS016 Revision 7

Reference: CS_WI_BS005

Effective Date: 01Nov2021

grade 1 for other symptoms)

- Doses without diary completed will be excluded

The number and percentage of participants with unsolicited AEs within 28 days after any doses with its exact 95% CI will be tabulated by system organ class and preferred term for each treatment group. Similar tabulation will be done for

- severe (grade 3) unsolicited AEs
- unsolicited AEs causally related to vaccination
- severe and causally related unsolicited AEs
- unsolicited AEs of special interest (AESIs)
- unsolicited AEs requiring medical attendance (MAAEs)

The incidence of solicited adverse events (local and systemic) with severity will be plotted using horizontal bar charts. For the purpose of this plot, severity will follow the definitions according to the [FDA Guidance for Industry: Toxicity Grading Scale for Healthy Adult and Adolescent Volunteers Enrolled in Preventive Vaccine Clinical Trials \(September 2007\)](#). For example, the result collected in eCRF will correspond to following severity grades:

Injection Site Pain:

Awareness of injection site pain, but easily tolerated: Mild or Grade 1

Injection site pain is affecting normal activities: Moderate or Grade 2

Unable to do normal activities, health is affected, and needs medication or visit: Severe or Grade 3

Systemic Events (Chills, Muscle Pains, Fatigue, Headache, Malaise, Nausea, Vomiting):

Awareness but easily tolerated: Mild or Grade 1

Affecting normal activities: Moderate or Grade 2

Unable to do normal activities: Severe or Grade 3.

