9.4.1 Safety Analysis

The percentage of participants with at least one solicited AE (local and systemic), with at least one unsolicited AE, and with any AE during the 7-day or the 28-day follow-up period will be tabulated after each vaccination and overall. Similar tabulation will be done for Grade 3 events, any AESIs, any MAAEs, any AEs considered related to the vaccination and any Grade 3 AEs considered related to vaccination.

The percentage of participants reporting each individual solicited local and general AE during the 7-day follow-up period will be tabulated over the three doses.

The percentage of participants with unsolicited AEs, including AESIs, MAAEs and SAEs within 28 days after any doses will be tabulated by treatment and by Medical Dictionary for Regulatory Activities (MedDRA) preferred term. Similar tabulation will be done for Grade 3 unsolicited AEs and for Grade 3 and causally related unsolicited AEs and for unsolicited AEs causally related to vaccination.

The number of participants who experienced at least one SAE during the entire study period will be reported. The number and percentage of participants with AESIs, MAAEs, AEs/SAEs, and ARs/SARs leading to withdrawal from the study or discontinuation of the treatment will be tabulated.

The number and percentage of participants with any SAE, AESIs, MAAEs, ARs/SARs leading to withdrawal from the study between Day 57 (28 days post second injection) to Day 168 and from 28 days after 3rd vaccination up to Day 365 will also be summarised by treatment group.

All laboratory test results, and vital signs measurements will be summarised for each treatment group using descriptive statistics at each visit for observed and change from baseline values. The incidence of treatment-emergent abnormal laboratory values will also be summarised using descriptive statistics.

Further details will be provided in the SAP.

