2. STUDY OBJECTIVES

2.1. Primary Objective

The primary objective is to evaluate the safety and tolerability of the GBS-NN/NN2 vaccine for 4 weeks after each dose of vaccine.

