3. STUDY ENDPOINTS

3.1. Primary Endpoints

- Safety and tolerability, as determined by the occurrence of adverse events (AEs) consisting of local and systemic reactogenicity, within 7 days after vaccination (Days 1 through 8 post each dose of investigational medicinal product (IMP))
- Unsolicited AEs, including AE of special interest (AESIs), medically attended AEs (MAAEs) and serious AEs (SAEs) within 28 days after each vaccination
- AESIs, MAAEs, adverse reactions (ARs)/serious adverse reactions (SARs) leading to withdrawal from study

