4.3. Changes to Analysis from Protocol

There are no changes to analyses from protocol.

Document: \\dccar2dnetvnasc01p-lan1.quintiles.net\cp_ops\BIOS\MinervaX\GBS-NN_NN2\MVX0006\Biostatistics\Documentation\SAP

Author: [REDACTED] Version Number: 1.0

Version Date: 19APR2024

Template No.: CS_TP_BS016 Revision 7

Reference: CS_WI_BS005

Effective Date: 01Nov2021

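### SAP 17.1 keeps the after-each-vaccination overview for solicited AEs only; the protocol's per-dose overview of unsolicited AEs and of any AE is missing from the SAP text, although SAP 4.3 declares no changes

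*SAP*

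**What the plan says.** The primary objective in SAP 2.1 is to "evaluate the safety and tolerability of the GBS-NN/NN2 vaccine for 4 weeks after each dose of vaccine". SAP 3.1 has three primary components. The second covers unsolicited AEs, including AESIs, MAAEs and "serious AEs (SAEs) within 28 days after each vaccination".

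Protocol 9.4.1 plans two separate outputs that matter here:

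- **An overview.** Its opening sentence starts with solicited AEs and goes on to participants "with at least one unsolicited AE, and with any AE during the 7-day or the 28-day follow-up period will be tabulated after each vaccination", with an overall result as well. It then adds: "Similar tabulation will be done for Grade 3 events, any AESIs, any MAAEs, any AEs considered related to the vaccination", and related Grade 3 AEs.
- **A preferred-term table.** A later paragraph plans unsolicited AEs in the 28 days after any dose, by MedDRA preferred term, with Grade 3 and related subsets.

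SAP 17.1 carries these forward as follows:

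- Solicited AEs, at least one: "solicited AE (local, systemic and any) during the 7-day solicited period will be tabulated by treatment group with exact 95% CI after each vaccination", plus an overall result. The word any in that phrase means any solicited AE.
- Individual solicited symptoms, by severity grade, over the three doses and also: "At each study dose (visit), the percentage of subjects with the symptom and its exact 95% CI".
- Unsolicited AEs: "The number and percentage of participants with unsolicited AEs within 28 days after any doses with its exact 95% CI will be tabulated" by SOC and PT, with severe, related, severe related, AESI and MAAE versions.

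SAP 4.3 states: "There are no changes to analyses from protocol".

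**The concern.** The primary objective and the unsolicited-AE component are both worded per dose. The only SAP output for that component pools the three doses. A participant with an event after dose 1 and a participant with an event after dose 3 fall in the same cell. The table therefore cannot show whether unsolicited events concentrate after one dose of a three-dose regimen, which the protocol overview would show. The any-AE row, which combines solicited and unsolicited events, does not appear in the SAP text at all, either per dose or overall.

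Because SAP 4.3 declares no changes, a reader of the SAP has no signal that a protocol-planned summary is missing and no reason for its absence.

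**Working it through.** The plan states no figure to reproduce, so the check compares protocol 9.4.1 with SAP 17.1, 17.1.1 and 17.1.2.

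**Step 1. Headline rows of the protocol overview against the SAP text**

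| Event type | After each of 3 doses | Overall |
|---|---|---|
| Solicited AE | present | present |
| Unsolicited AE | absent | no overview row; the pooled SOC/PT table covers the same window |
| Any AE | absent | absent |

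Cells per treatment group: 3 event types × (3 doses + 1 overall) = 12. Present: 3 + 1 = 4. Absent: 3 (unsolicited, per dose) + 4 (any AE) = 7. The remaining cell, unsolicited overall, can be read from the pooled table if that table has an at-least-one row, which the text does not say.

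**Step 2. Subset rows.** The protocol names five: Grade 3, AESI, MAAE, related, related Grade 3. SAP 17.1 has each for unsolicited AEs pooled over doses, and none after each vaccination. The one per-dose severity output is for individual solicited symptoms.

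**Step 3. Do other SAP sections fill the gap?** SAP 17.1.1 covers events leading to withdrawal or discontinuation, and the long-term windows. SAP 17.1.2 covers SAE listings and the same long-term windows. Neither gives a per-vaccination table of unsolicited AEs or an any-AE table.

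**Step 4. What a pooled count can and cannot say.** If k participants have an event after any dose, the count after a given dose lies between 0 and k. Assume, for illustration, an active healthy arm of 24 (protocol 9.2), all doses received, and k = 6. The pooled result is 6/24 = 25.0% (Clopper-Pearson 95% CI 9.8 to 46.7). A single dose could then be anything from 0/24 (upper limit 1 − 0.025^(1/24) = 14.2%) to 6/24. The count is invented and the bound holds for any pooled count, so this shows what kind of information is lost and says nothing specific about this trial.

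**Step 5. Can the per-dose table be derived?** SAP 7.4.1 attributes each event to the most recent dose before its start. It sets no time limit, so it needs the 28-day limit added. From the schedule of activities, dose 2 is at Day 29 ± 3 (Day 26 to 32) and dose 3 at Day 169 ± 7 (Day 162 to 176):

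- Dose 1 to dose 2: 26 − 1 = 25 to 32 − 1 = 31 days. Where the gap is under 28 days, 7.4.1 settles the overlap by assigning the event to dose 2.
- Dose 2 to dose 3: 162 − 32 = 130 to 176 − 26 = 150 days. Without a limit, 7.4.1 attributes this whole interval to dose 2.

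Protocol 8.3.1 collects only MAAEs, AESIs and SAEs from Day 58 to Day 161, and again after Day 197. The limit therefore matters mainly for those event types. It also affects ordinary AEs that start between Day 162 and dose 3.

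**The case against.** The strongest reply is that SAP 9 assigns the format and content of tables to templates supplied with the SAP, and those were not among the documents available. An AE overview table with per-dose rows may be there. The attribution rule in SAP 7.4.1 points the same way: solicited AEs come from a diary kept after each vaccination and hardly need such a rule, so its natural use is for unsolicited events. This stands as a limit. It is a reason to say that the SAP text omits the overview, and it rules out saying that the overview will not be produced.

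A reader might infer more from two other sections. SAP 4.3 could be read as proof that the analysis was silently dropped, but it can equally mean that protocol 9.4.1 remains in force. SAP 5.2 says that analyses identified in the SAP will be performed; it does not say that no others will be. Neither supports a claim of deliberate removal.

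It is also fair that much is retained. The any-dose SOC/PT tables follow the protocol's own paragraph on unsolicited AEs. Solicited AEs keep their per-dose results. Protocol 9.4 plans individual data listings, and SAP 7.4 puts study day in every listing with an event date. In groups of 6 to 24, a reader could reconstruct the timing by hand. But listings preserve the data without giving the percentages that the protocol promises.

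Finally, a reader might infer that the primary safety result would be biased. The documents do not support that: no hypotheses are tested (protocol 9.1) and SAP 17 plans no between-group comparisons of safety data.

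**Conclusion.** The point holds for the SAP text. Followed as written, SAP 17.1 leaves the unsolicited-AE component of the primary endpoint without its protocol-planned result after each vaccination, and leaves out the any-AE summary entirely, while SAP 4.3 says nothing has changed. The consequence is an omitted descriptive summary of one of three primary safety components. No estimate that the SAP does plan is affected.

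Two assumptions carry this: that the unseen templates do not already contain the table, and that the protocol's overview and its preferred-term table are separate outputs. The second is clear from protocol 9.4.1, which puts them in different paragraphs with different time splits. The first cannot be checked from the documents. The matter is worth correcting because it concerns a primary component and the repair is small.

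**What to change.** In SAP 17.1 add one table by treatment group:

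- **Unsolicited rows.** Number and percentage of participants with at least one unsolicited AE, and with each protocol 9.4.1 subset (Grade 3, AESI, MAAE, related, related Grade 3), within 28 days after dose 1, dose 2, dose 3 and overall. The per-dose denominator is participants who received that dose. Attribute events by SAP 7.4.1, limited to 28 days after the dose.
- **Any-AE rows.** The same columns, for the 7-day and the 28-day periods that the protocol names. State the denominator, and make it consistent with the SAP 17.1 rule that excludes doses without a completed diary from the solicited analysis. Using everyone dosed would count a missing diary as no solicited event. One consistent choice is participants dosed with a completed diary for that dose, with the number excluded shown.
- **Confidence intervals.** Protocol 9.4.1 does not require exact intervals for these rows. They are optional, for consistency with the other SAP 17.1 tables.

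If a template already holds this table, cite it in 17.1. If the omission is intended, declare and justify it in SAP 4.3.

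The cost is a short SAP addition and one summary table, or one cross-reference. No new data are needed.

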9.4 Statistical Analyses

The statistical analysis plan (SAP) will be developed and finalised before database lock and will describe the participant analysis sets to be included in the analyses, and procedures for accounting for missing, unused, and spurious data. This section is a summary of the planned statistical analyses of the primary and secondary endpoints.

All analyses, summaries, and listings will be performed using the SAS® software (version 9.4 or higher).

The following descriptive statistics will be used as applicable to summarise the study data unless otherwise specified:

- Continuous variables: sample size [n], mean, standard deviation [SD], median, minimum [min], and maximum [max].
- Categorical variables: frequencies and percentages.

Individual participant data will be presented in listings.

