9.4.3 Missing Data

Missing data will not be imputed.

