8. STATISTICAL CONSIDERATIONS

8.1. Missing Data

Missing safety data will not be imputed.

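### SAP 17.1 fills a missing solicited-symptom severity with the lowest grade, against the no-imputation statements, and its text asks for no count of the reports affected

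*SAP*

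**What the plan says.** SAP 17.1 plans tables of each individual solicited local and systemic event that "will be tabulated by treatment group and severity grade with exact 95% CI as follows", both over the three doses and at each dose. It also plans bar charts of the same events by severity.

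On missing entries, the section first states that "missing or non-evaluable measurements will not be replaced". It then lists specific rules:

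- A symptom with full or partial daily recording is "classified according to their maximum observed daily recording over the solicited period".
- A symptom reported present "without having recorded any daily measurement will be assigned to the lowest intensity category at that dose". The category is 38°C for fever and Grade 1 for every other symptom.
- A dose with no completed diary drops out of the analysis.

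The general statements are shorter. SAP 8.1 says "Missing safety data will not be imputed" and protocol 9.4.3 says "Missing data will not be imputed". Protocol 9.4 hands to the SAP the "procedures for accounting for missing, unused, and spurious data", and also says "Individual participant data will be presented in listings".

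For fever, protocol 8.3.5 (Table 4, footnote a) tells investigators to record a fever reported without a thermometer reading as an elevated temperature.

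**The concern.** A symptom known to be present with no recorded intensity has a missing severity. Assigning it Grade 1 replaces the missing value with a fixed one, and that value is the mildest available. A reader who takes SAP 8.1 at its word would conclude that every grade in the tables was observed, which need not be so.

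Reactogenicity is part of the primary endpoint (SAP 3.1), severity by grade is a planned table, and protocol 9.4.1 plans a separate Grade 3 tabulation. The SAP text provides no category for unrecorded severity and asks for no count of reassigned reports. Someone reading the summary tables therefore could not separate a mild reaction from one of unknown intensity. In groups of 6 to 24, one participant is enough to change a Grade 3 row from empty to not empty.

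**Working it through.** **Text comparison.** The plan gives no figure to reproduce here, so the check starts from the wording.

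| Place | Instruction for a missing severity |
|---|---|
| Protocol 9.4.3 | no imputation, no exception named |
| SAP 8.1 | no imputation of safety data, no exception named |
| SAP 17.1, general sentence | not replaced |
| SAP 17.1, specific rule | set to 38°C or Grade 1 |

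The last line does what the other three rule out. Protocol 9.4 lets the SAP set such a rule, so the fault is the disagreement and not the SAP's authority.

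**Direction at a single dose.** For one symptom in one group, let u2 and u3 be the numbers of ungraded participants whose reaction was really Grade 2 or Grade 3. Then:

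- tabulated Grade 3 = actual Grade 3 − u3
- tabulated Grade 2 = actual Grade 2 − u2
- tabulated Grade 1 = actual Grade 1 + u2 + u3

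Since u2 and u3 cannot be negative, the rule leaves the Grade 2 and Grade 3 rates correct or too low.

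**Direction over three doses.** Take each participant's highest grade. An ungraded Grade 3 at one dose with an observed Grade 2 at another is counted as Grade 2, so Grade 2 alone can move either way. Grade 3, and Grade 2 or higher, can still only be correct or too low.

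**Any grade.** Presence is documented, so these rates do not change. Fever is the possible exception. A fever without a reading receives 38°C under the SAP, above the protocol's cutoff of 37.9°C, whereas footnote a has it recorded as something other than fever. The any-fever count is too high only if such a report was not recorded as the footnote says.

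**Size.** Planned group sizes come from protocol 9.2, with placebo pooled as in SAP 7.2:

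- healthy active: 24 and 24
- healthy placebo: 6 + 6 = 12
- obese/diabetic active: 12 and 12
- obese/diabetic placebo: 3 + 3 = 6

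One participant moves a rate by 100/n points: 100/24 = 4.2, 100/12 = 8.3, 100/6 = 16.7.

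Actual sizes may fall either side of plan. With one fewer or one more (an assumed range), the steps are:

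- 100/23 = 4.3 to 100/25 = 4.0
- 100/11 = 9.1 to 100/13 = 7.7
- 100/5 = 20.0 to 100/7 = 14.3

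Exact limits use the Clopper-Pearson method of SAP 7.1. For x of n, the lower limit is the 2.5% quantile of Beta(x, n−x+1), or 0 if x = 0. The upper limit is the 97.5% quantile of Beta(x+1, n−x). Suppose a Grade 3 row reads zero and no other Grade 3 was observed. The numbers of hidden Grade 3 participants below are assumed for illustration.

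| n | Row as tabulated | One hidden Grade 3 | Two hidden Grade 3 |
|---|---|---|---|
| 24 | 0% (0 to 14.2) | 4.2% (0.1 to 21.1) | 8.3% (1.0 to 27.0) |
| 12 | 0% (0 to 26.5) | 8.3% (0.2 to 38.5) | 16.7% (2.1 to 48.4) |
| 6 | 0% (0 to 45.9) | 16.7% (0.4 to 64.1) | 33.3% (4.3 to 77.7) |

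The unit is the participant, not the report.

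**The case against.** The strongest reply is that the section resolves itself. The bullets are introduced as the detail of the general sentence, each situation has one instruction, a programmer would not be in doubt, and the protocol delegates the matter to the SAP. On that view only a cross-reference in SAP 8.1 is missing. This is right about programming. It does not remove the conflict, because the bullet reverses the sentence it is meant to detail.

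A second reply is that the rule may hardly ever apply. Protocol 8.2.4 has participants record intensity for the systemic symptoms, and SAP 17.1 maps collected answers directly to grades, so a symptom marked present may usually arrive with its grade. Site staff also assess the diary reactions, and investigators rate intensity under protocol 10.3.3. A severe reaction left ungraded at every step would be unusual. This stands as a limit on size. However, the documents do not say whether a site-assessed intensity counts as recorded before the rule applies.

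Third, the output templates mentioned in SAP 9 are not among the documents and may already footnote or count these reports, and individual listings are planned. That is a fair limit on the claim about the tables.

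Fourth, the fever discrepancy matters only if footnote a is not followed. That also stands. The two passages still describe the same report differently.

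**Conclusion.** The concern holds, as a minor point. The conflict between SAP 17.1 and the no-imputation statements is plain from the text. The one-way effect on Grade 3, and on Grade 2 or higher, follows from the rule without any assumption about the data.

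The practical effect is unknown and may be nil. It is confined to symptoms with no daily entry at all on a dose whose diary counts as completed. The tabulated percentages and intervals above are worst cases, not forecasts. They assume planned group sizes, an actual Grade 3 reaction, and no other observed Grade 3 for that participant in the row.

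That the summary tables hide these reports rests on the SAP text alone, since the templates were not available. The rule applies to every group and no safety comparisons are planned (SAP 17), so there is no claim that it favours the vaccine.

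**What to change.** 1. Replace the lowest-category rule with a table row for symptoms present with severity not recorded. Keep these participants in the any-grade rate and report their number by group and dose. A line counting them as Grade 3, labelled as an upper bound, is optional.
2. State whether a severity assessed by the site counts as recorded.
3. Reconcile the SAP's 38°C rule with protocol Table 4 footnote a.
4. If the sponsor prefers to keep the rule, name it as an exception in SAP 8.1 and report the reassigned counts by group and dose. If the templates already show these counts, only the wording needs changing.

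The cost is SAP wording plus one row, or one footnote with counts, per solicited-event severity table. No new data are needed, and any-grade rates do not change except possibly for fever.

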8.2.4 Electronic Diary

The participant will get access to an eDiary at Visit 2, when vaccine/placebo is administered. In the eDiary, the participant is asked to record details of solicited local and systemic reactions for 7 days after each of the vaccinations (the day of the vaccination and the following 6 days).

For solicited local injection site reactions (redness, swelling, pain, tenderness, itching) and pyrexia (oral temperature $>37.9^{\circ}\text{C}$), the diameters and temperatures will be measured by the participant, by use of rulers and thermometers, and recorded in the eDiary.

For solicited systemic reactions (chills, muscle pains/myalgia, malaise, nausea, vomiting, headache, and fatigue), intensities (mild, moderate, or severe) should be recorded in the eDiary by the participant. In addition, other AEs, ie, unsolicited AEs, including medically attended AEs (MAAEs), SAEs, CM and/or vaccines should also be recorded and assessed in the eDiary.

The solicited local and systemic reactions, and CMs recorded in the eDiary, will be assessed by the site staff.

If serious, the SAEs will undergo evaluation as per the current reference safety information of the IB, as described in Section [6.0](#).

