8.3.4 Regulatory Reporting Requirements for SAEs

Prompt notification by the investigator to the Sponsor or designee of an SAE is essential so that legal obligations and ethical responsibilities toward the safety of participants and the safety of an IMP under clinical investigation are met.

The Sponsor has a legal responsibility to notify both the local regulatory authority and other regulatory agencies about the safety of an IMP under clinical investigation. The Sponsor will comply with country-specific regulatory requirements relating to safety reporting to the regulatory authority, EU Eudravigilance Database (as applicable), IRBs/IECs, and Investigators.

An investigator who receives an investigator safety report describing an SAE or other specific safety information (eg, summary or listing of SAEs) from the Sponsor will review and then file it along with the IB and will notify the IRB/IEC, if appropriate according to local requirements.

Investigator safety reports must be prepared for SUSARs according to local regulatory requirements and Sponsor policy and forwarded to Investigators as necessary.

8.3.5 **Solicited Adverse Events**

Local and systemic predefined solicited AEs for reactogenicity assessment will be collected by the participant in a solicited AE eDiary for 7 days following each study vaccination. The set of solicited AEs associated with reactogenicity are presented in Table 4.

Table 4 Reactogenicity Assessment: List of solicited adverse events

Local	Systemic
Pain at the site of injection	Fever (>100°F [>37.9°C]) ^a
Erythema/redness at the site of injection	Chills
Tenderness	Muscle pains
Induration/swelling at the site of injection	Fatigue
Itching	Headache
	Malaise
	Nausea
	Vomiting

^a Fever measured orally. Investigators who consider a temperature lower than this cutoff as a fever or a ‘fever’ reported by participants without documentation by a thermometer should record the event as ‘elevated body temperature’.

8.3.6 **Adverse Events of Special Interest and Medically Attended Adverse Events**

Adverse events will be monitored throughout the study to identify any event of interest that may indicate a trend or risk to participants. The following are considered adverse events of special interest (AESI):

- Development of autoimmune diseases
- GBS infections
- Symptomatic GBS urinary tract infections

A MAAE is an AE that leads to an unscheduled visit to a health care provider.

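### SAP 17.1 counts a fever reported with no temperature reading as a 38°C solicited fever, whereas protocol Table 4 footnote a sends it to 'elevated body temperature'

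*SAP*

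**What the plan says.** Protocol 8.3.5, Table 4, lists fever among the solicited systemic events with a numeric definition, "Fever (>100°F [>37.9°C", measured orally. Footnote a covers the case with no reading: investigators faced with a 'fever' "reported by participants without documentation by a thermometer should record the event as" elevated body temperature. That term does not appear in Table 4. Protocol 8.2.4 likewise treats pyrexia as a measured item: "temperatures will be measured by the participant, by use of rulers and thermometers, and recorded in the eDiary".

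SAP 17.1 gives counting rules for solicited events. A participant who documents a symptom "without having recorded any daily measurement will be assigned to the lowest intensity category at that dose (i.e. 38°C for fever", or to grade 1 for other symptoms. The lead-in to the same rules says that "missing or non-evaluable measurements will not be replaced". SAP 8.1 says "Missing safety data will not be imputed", and protocol 9.4.3 likewise rules out imputation of missing data.

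SAP 3.1 defines the first primary endpoint as adverse events "consisting of local and systemic reactogenicity, within 7 days after vaccination", which includes fever. SAP 4.3 says "There are no changes to analyses from protocol".

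**The concern.** For most solicited symptoms the lowest-intensity rule supplies only a missing grade: the participant has said the symptom occurred, and the report itself makes the case. Fever is different. It is the only systemic event in Table 4 with a numeric cut-off, so assigning a temperature above that cut-off decides whether there is a case at all.

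The two documents therefore give different answers for the same record, a fever reported with no reading on any day. The record affects the fever row per dose and over three doses, and the severity bar chart. If the participant has no other event, it can also affect the rows for any systemic and any solicited event. The trial tests no hypotheses (protocol 9.1), so these descriptive rates are themselves the primary result. A reader of the fever table would assume the protocol's definition, because the SAP declares no departure from it.

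**Working it through.** The documents give no fever rate or count of unmeasured reports, so there is no stated figure to reproduce. The check has two parts.

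**1. The same record under each text.** The record is fever marked as present, with no temperature on any day of the solicited period.

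- Protocol Table 4, footnote a: no thermometer documentation, so it should be recorded as elevated body temperature. Contribution to solicited fever: 0.
- SAP 17.1: presence documented and no measurement, so 38°C is assigned. Since 38 > 37.9, contribution to solicited fever: 1.
- SAP 17.1 lead-in, SAP 8.1 and protocol 9.4.3: no replacement or imputation. No temperature exists to compare with the cut-off.

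Relative to the protocol definition, the SAP rule can add fever cases and cannot remove any.

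**2. Size per affected participant.** The inputs are:

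- Planned sizes (protocol 9.2): 24 active and 6 placebo in each healthy cohort; 12 active and 3 placebo in each obese/diabetic cohort.
- Placebo pooling within population (SAP 7.2): 6 + 6 = 12 healthy and 3 + 3 = 6 obese/diabetic.
- Interval method (SAP 7.1): two-sided 95% Clopper-Pearson.

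Each affected participant with no other fever adds 1/n. For 0 cases the upper limit is 1 − 0.025^(1/n), for example 1 − 0.025^(1/12) = 26.5%. For 1 case the limits are the 2.5% point of Beta(1, n) and the 97.5% point of Beta(2, n − 1).

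| Group | n | Added by one participant | 0 cases (95% CI) | 1 case (95% CI) |
|---|---|---|---|---|
| Healthy active, each dose level | 24 | 1/24 = 4.2 points | 0% (0 to 14.2) | 4.2% (0.1 to 21.1) |
| Obese/diabetic active, each dose level; healthy placebo pooled | 12 | 1/12 = 8.3 points | 0% (0 to 26.5) | 8.3% (0.2 to 38.5) |
| Obese/diabetic placebo pooled | 6 | 1/6 = 16.7 points | 0% (0 to 45.9) | 16.7% (0.4 to 64.1) |

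This takes all planned participants as the denominator. SAP 17.1 excludes doses without a completed diary, so a real denominator could be smaller and the step larger.

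**How often it might happen.** This rests on an assumption only. Suppose each dose carries a probability q of an unmeasured fever report, independently over three doses. The chance of at least one affected participant is then 1 − (1 − q)^(3n). For q from 0.5% to 5% this runs from 30% to 98% at n = 24, 17% to 84% at n = 12, and 9% to 60% at n = 6. Nothing in the documents supports any particular q, and q could be zero.

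**The case against.** The strongest reply is that the two rules act at different stages. The footnote tells investigators how to record an event; SAP 17.1 tells the programmer how to count a symptom already documented as present. In between, site staff review the diary and transfer relevant events to the eCRF (protocol 6.6) and assess the solicited reactions (protocol 8.2.4). SAP 17.1 itself refers to results collected in the eCRF when it describes severity grading. If staff apply the footnote, the fever clause may have nothing to act on. This stands as a limit on how often the rule would fire. It does not remove the conflict, because the documents never say whether the tables use raw or staff-reviewed entries, and the clause explicitly provides for fever with no reading.

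It is also fair that the protocol leaves missing-data procedures to the SAP (9.4), so a counting convention is not plainly a change of analysis. But this convention alters the case definition of a listed event and runs against the SAP's own text, so it should at least be stated openly.

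The consequences are bounded. Safety data are not compared between groups (SAP 17). An assigned 38°C cannot meet the febrile criterion of >38.5°C in protocol 4.6.3, and Safety Review Group reporting is outside the SAP (5.1). Counting more reactogenicity may look cautious, but the rule applies equally to placebo, so it does not reliably make the vaccine look worse.

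A reader might infer more than the documents support:

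- *That the fever rate is inflated as a matter of fact.* This needs at least one unmeasured report to reach the tables as fever. Some such reports may be true fevers, so any excess is against the protocol definition, not necessarily against the truth.
- *That the protocol declares such a report not to be fever.* The footnote says 'should' and names another term. Exclusion from solicited fever is a reasonable inference from that, not a stated prohibition.
- *That one report will be counted twice, as solicited fever and as a separate event.* That requires both the diary entry and the relabelled entry to feed the outputs, which no section says.

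**Conclusion.** The conflict holds on the text. SAP 17.1 can make a solicited fever case out of a report that protocol Table 4 sends elsewhere, it contradicts the SAP's own no-replacement and no-imputation statements, and it is not declared in SAP 4.3. The effect is conditional: 4.2, 8.3 or 16.7 percentage points per affected participant at n = 24, 12 or 6, assuming full planned denominators, no other fever in that participant, and a data flow in which the report reaches the tables as fever. The number of affected participants is unknown and may be zero. The point is worth correcting because fever is a component of the primary reactogenicity endpoint, the groups are small enough for one record to be visible, and the correction is simple.

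**What to change.** In SAP 17.1:

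1. Exempt fever from the lowest-intensity rule.
2. Count solicited fever only where at least one recorded oral temperature exceeds the protocol cut-off. This also settles a point the SAP leaves open: how to treat a fever marked as present whose recorded maximum is below the cut-off.
3. Tabulate fevers reported without any recorded temperature once, in a separate row for elevated body temperature.
4. State whether that row enters the totals for any systemic and any solicited event.
5. State whether the solicited-event tables use raw eDiary entries or staff-reviewed entries.

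The cost is a short text change, one derivation condition and one table row; no new data are needed. The drawback is that a true fever nobody measured leaves the fever row. It stays visible in the separate row, and a sensitivity count that adds these reports back can be given. If the sponsor prefers to keep the 38°C convention, it should be declared in SAP 4.3, reconciled with the lead-in to 17.1 and with 8.1, and accompanied by a count that excludes unmeasured reports.
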